9.1.4.7 Digital Ulcer Count

The digital ulcer count captures the number of active open sores (or digital ulcers) on fingertips secondary to SSc (and not secondary to localized trauma or injury). Cracks, fissures or even skin breakdown related to calcinosis should not be included. The digital ulcer count will be conducted at all visits except V1 and V3.

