The digital ulcer count corresponds to the sum of active or new plus indeterminate/healing digital ulcers secondary to SSc (see [Appendix I](#)).

- CRISS.

The Composite Response Index for Diffuse Cutaneous Systemic Sclerosis (CRISS) tool summarizes the changes in the clinical and patient-reported outcomes using a single composite score that reflects the probability that the patient with dcSSc has improved.

CRISS is obtained in a 2-step process as described below.

Step 1: Patients who develop new or worsening of cardiopulmonary and/or renal involvement due to SSc are considered as not improved (irrespective of improvement in other core items) and assigned a probability of improving equal to 0.0. Specifically if a subject develops any of the following:

- New scleroderma renal crisis.
- Decline in FVC% predicted $\geq 15\%$ (relative), confirmed by another FVC% within a month, high resolution computer tomography (HRCT) to confirm ILD (if previous HRCT of chest did not show ILD) and FVC% predicted below 80% predicted*.
- New onset of left ventricular failure (defined as left ventricular ejection fraction $\leq 45\%$) requiring treatment*.
- New onset of Pulmonary Arterial Hypertension (PAH) on right heart catheterization requiring treatment*. PAH is defined as mean pulmonary artery pressure ≥ 25 mm Hg at rest and an end-expiratory pulmonary artery wedge pressure ≤ 15 mm Hg and a pulmonary vascular resistance > 3 Wood units.

*Attributable to SSc

Step 2: For the remaining patients, Step 2 involves computing the predicted probability of improving for each subject using the following equation (equation to derive predicted probabilities from a logistic regression model):

$$\frac{\exp(-5.54-0.81*\Delta\text{MRSS}+0.21*\Delta\text{FVC\%}-0.40*\Delta\text{Pt-glob}-0.44*\Delta\text{MD-glob}-3.41*\Delta\text{HAQ-DI})}{1+\exp(-5.54-0.81*\Delta\text{MRSS}+0.21*\Delta\text{FVC\%}-0.40*\Delta\text{Pt-glob}-0.44*\Delta\text{MD-glob}-3.41*\Delta\text{HAQ-DI})}$$

ΔmRSS indicates the change in mRSS from baseline, $\Delta\text{FVC\%}$ denotes the change in FVC% predicted from baseline, $\Delta\text{Pt-glob}$ indicates the change in patient global assessment (as per Likert scale), $\Delta\text{MD-glob}$ denotes the change in physician global assessment (as per Likert scale) (see [Appendix G](#)), and $\Delta\text{HAQ-DI}$ is the change in HAQ-DI. All changes are absolute change ($\text{Time}_2 - \text{Time}_{\text{baseline}}$).

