2.4.4.4.5 Digital ulcer count

Change in digital ulcer count (sum of active or new plus indeterminate/healing digital ulcers secondary to SSc) from baseline to Week 24 and from baseline to Week 35 will be analyzed using the MMRM model described in [Section 2.4.4.4](#).

The digital ulcer count, as well as the subcategories: number of active/new ulcers and number of indeterminate/healing ulcers, will also be descriptively summarized by treatment group and by time point.

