Appendix G Patient and physician global assessments of overall health using the 0-10 Likert scale

Appendix H TJC28

Appendix I Digital ulcer count

ACT14604/SAR156597
Digital Ulcer Count Source Document

Patient No. (12 digits):
Country No. Centre No. Subject No.

Visit Name: V2/Baseline

Investigator Initials: _____

Visit Date: / /
DD MM YYYY

V2/BASELINE

LEFT HAND

Ulcer Location*	Ulcer Status	
	Active	Indeterminate / Healing
		
Total Number of Ulcers for CRF		

*Please enter the number corresponding to ulcer location

RIGHT HAND

Ulcer Location*	Ulcer Status	
	Active	Indeterminate / Healing
		
Total Number of Ulcers for CRF		

*Please enter the number corresponding to ulcer location

For an ulcer that encompasses two adjacent locations (e.g., Right hand, locations 2 and 3), please select one of the two locations where the majority of the ulcer is present and record it under this location. (Such an ulcer should not be recorded separately in two different locations.) For all subsequent assessment of the same ulcer, please continue to record the ulcer using this same location.

ACT14604/SAR156597
Digital Ulcer Count Source Document

Patient No. (12 digits):
Country No. Centre No. Subject No.

Visit Name: _____

Investigator Initials: _____

[figure not shown]
Visit Date: / /
DD MM YYYY

ALL VISITS EXCEPT V2/BASELINE

LEFT HAND

Ulcer Location*	Ulcer Status		
	Active ⁽¹⁾	New ⁽²⁾	Indeterminate / Healing ⁽³⁾
			
			
			
			
			
			
			
			
Total Number of Ulcers for CRF			

*Please enter the number corresponding to ulcer location

RIGHT HAND

Ulcer Location*	Ulcer Status		

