	Active ⁽¹⁾	New ⁽²⁾	Indeterminate / Healing ⁽³⁾
			
			
			
			
			
			
			
Total Number of Ulcers for CRF			

*Please enter the number corresponding to ulcer location

For an ulcer that encompasses two adjacent locations (e.g., Right hand, locations 2 and 3), please select one of the two locations where the majority of the ulcer is present and record it under this location. (Such an ulcer should not be recorded separately in two different locations.) For all subsequent assessment of the same ulcer, please continue to record the ulcer using this same location.

- 1) Active ulcers: already present at last visit
- 2) New ulcers: not present at last visit, regardless of their current status (active, indeterminate/healing or healed)
- 3) Indeterminate/Healing: already present at last visit

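### The SAP's digital ulcer count can include healed ulcers after baseline but not at baseline, so its change score sets a point count against a partly interval count and departs from the protocol's active-ulcer count

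*SAP*

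**What the plan says.** Protocol 9.1.4.7 says that the count "captures the number of active open sores (or digital ulcers) on fingertips secondary to SSc". It is taken at every visit except V1 and V3, that is, at baseline and Weeks 4, 8, 12, 24 and 35. That section does not mention healing, indeterminate or healed ulcers.

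SAP 2.1.4 gives a wider definition: "The digital ulcer count corresponds to the sum of active or new plus indeterminate/healing digital ulcers secondary to SSc". SAP 2.4.4.4.5 makes this sum the analysis variable, "Change in digital ulcer count (sum of active or new plus indeterminate/healing digital ulcers secondary to SSc) from baseline to Week 24", and does the same for Week 35. Appendix B lists the same MMRM. Both places add descriptive tables of two subcategories: active and new pooled, and indeterminate/healing.

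Appendix I holds two source forms. The one marked "Visit Name: V2/Baseline" has two status columns, Active and Indeterminate/Healing. The one marked "ALL VISITS EXCEPT V2/BASELINE" has a third column, New. Its footnote defines that column: "New ulcers: not present at last visit, regardless of their current status (active, indeterminate/healing or healed"). The footnotes for Active and for Indeterminate/Healing restrict both to ulcers already seen at the previous visit.

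SAP 1.6, which lists changes made in the current SAP version, does not mention the ulcer definition. SAP 2.4.4.3 makes p-values for exploratory endpoints descriptive.

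**The concern.** A change score should subtract like from like. Here the baseline term counts ulcers present on the day. The follow-up term counts those, plus any ulcer that arose and healed since the previous visit. Patients with unchanged disease can then show a rise, and the possible rise depends on the visit gap. The gap is longest at Week 24, the time point of the main ulcer analysis.

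The sum also differs from the protocol's count in a second way. It includes ulcers that are healing, so an ulcer that moves from active to healing scores no change. What is at stake is whether the reported change in ulcer count can be read as the protocol describes it.

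**Working it through.** The documents state no figure for this endpoint, so there is nothing to reproduce. The check is a comparison of definitions, followed by counting and one illustration on assumed inputs.

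**1. Where each ulcer is recorded, and what it adds to the SAP sum**

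| State at the visit | Baseline form | Follow-up form | Protocol count |
|---|---|---|---|
| Open | Active, 1 | Active if seen at last visit, otherwise New, 1 | 1 |
| Indeterminate or healing | Indeterminate/Healing, 1 | Indeterminate/Healing if seen at last visit, otherwise New, 1 | 0 on a plain reading |
| Healed, arose since last visit | no column, 0 | New, 1 | 0 |
| Healed, seen at last visit | no column, 0 | no column, 0 | 0 |

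Only the third row scores differently at baseline and follow-up. Healing ulcers score 1 at both times, so they depart from the protocol wording but do not create the baseline mismatch.

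**2. Counting in hypothetical patients**

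*Patient A.* Baseline: 1 active and 1 healing. By Week 24 both have gone, and 2 new ulcers have appeared and healed since Week 12.
- SAP sum: 2 − 2 = 0
- Protocol, active only: 0 − 1 = −1
- Active plus healing by current status: 0 − 2 = −2

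*Patient B.* Baseline: 1 active. At Week 24 the same ulcer, seen at Week 12, is healing.
- SAP sum: 1 − 1 = 0
- Active only: 0 − 1 = −1

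**3. Look-back for New**

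Taking the last visit to mean the last one with an ulcer count, the gap is about 4 weeks at Weeks 4, 8 and 12, then 24 − 12 = 12 weeks at Week 24 and 35 − 24 = 11 weeks at Week 35.

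**4. Illustration (inputs assumed, not from the documents)**

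Assume stable disease, onset rate L = 0.1 ulcers per patient-week, each ulcer visible (open or healing) for D weeks, look-back T weeks, and every healed interval ulcer recorded. The expected baseline count is L × D. The expected excess from healed New ulcers is L × max(0, T − D) if duration is fixed, or L × [T − D(1 − e^(−T/D))] if it is exponential. For example, with T = 12 and D = 4 the fixed case gives 0.1 × (12 − 4) = 0.80.

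| D (weeks) | Baseline count | T = 4 (fixed / exp.) | T = 12, Week 24 (fixed / exp.) | T = 11, Week 35 (fixed / exp.) |
|---|---|---|---|---|
| 4 | 0.4 | 0 / 0.15 | 0.80 / 0.82 | 0.70 / 0.73 |
| 8 | 0.8 | 0 / 0.09 | 0.40 / 0.58 | 0.30 / 0.50 |
| 12 | 1.2 | 0 / 0.06 | 0 / 0.44 | 0 / 0.38 |

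The excess is proportional to L, so the absolute values carry no weight. The pattern does: it is small at the 4-week visits and largest at Week 24, and it shrinks as ulcers last longer.

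**5. Would the planned active/new subcategory serve instead?**

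*Patient C.* Baseline: 1 healing ulcer. By Week 24 it has gone, and one ulcer first seen at that visit is already healing.
- SAP sum: 1 − 1 = 0
- Active/new: 1 − 0 = +1, because a first-seen healing ulcer is New after baseline but Indeterminate/Healing at baseline
- Active plus healing by current status: 1 − 1 = 0

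Switching to active/new can create a rise that the SAP sum does not show.

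**The case against.** The strongest reply concerns impact. The same forms and rules apply to both blinded arms, and the analysis is a between-arm difference. A reader might infer that the treatment comparison is biased; the documents do not support that. An upward shift common to both arms cancels, and fewer new ulcers, even ones since healed, would still be a treatment effect. This stands. It assumes similar visit patterns, since an extra premature end-of-treatment visit (Protocol 10.3.4) shortens the next look-back, but nothing in the documents points to an imbalance.

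Second, the protocol never separates active from healing, and a healing ulcer may still be open. This stands in part. The departure is arguable for healing ulcers and clear for healed ones. A reader might also blame healing ulcers for the baseline mismatch; they do not cause it, because both forms count them.

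Third, the subcategory tables would show ulcers moving from active to healing. That is true descriptively. But active and new are pooled, so healed New ulcers stay hidden and no planned table returns the protocol's count.

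Fourth, the silence of SAP 1.6 proves little, because that list covers only the current SAP version. This also stands. The point rests on the two definitions not being reconciled in the documents as they are.

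**Conclusion.** The defect is in the text. A healed ulcer can add 1 to a follow-up count and cannot add 1 at baseline, so the change score mixes a point count with a partly interval count. The resulting count is not the protocol's count of active open sores. Counting healing ulcers is a separate, milder departure that can mute an active-to-healing improvement.

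The size is unknown. The documents give no ulcer incidence, duration or baseline prevalence, and the excess of 0 to about 0.8 ulcers at Week 24 shown above follows from an assumed onset rate and full recording of healed ulcers. Any stronger statement about magnitude would only restate an assumption.

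The consequence is confined to one exploratory endpoint with descriptive p-values, which does not enter the primary endpoint, the secondary endpoints or CRISS. Within-arm change is hard to interpret. The between-arm difference is not shown to be biased, but it mixes ulcers present at the visit with ulcers that arose and healed before it.

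**What to change.** In SAP 2.1.4, 2.4.4.4.5 and Appendix B:

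- Define the MMRM count by current status at each visit, with the same categories at baseline and follow-up: either active only, as in Protocol 9.1.4.7, or active plus indeterminate/healing. Exclude healed ulcers in either case.
- Do not simply move the MMRM to the pooled active/new subcategory.
- Report ulcers new since the last visit separately, as incidence, with the look-back stated.
- Declare any departure from the protocol definition.

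The cost is SAP wording plus a data check. No extra visits are needed. The difficulty is that the current status of each New ulcer is required, and the printed form has no field for it. If it was not captured, present Active + Indeterminate/Healing without New and with New, as lower and upper bounds for ulcers present at the visit, and state the limitation. These bounds hold for each patient's count and for simple arm means. Bounds for the between-arm difference come from crossing them, the lower value in one arm against the upper value in the other.

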2.1.5 Safety endpoints

The safety analysis will be based on the reported adverse events and other safety information, such as clinical laboratory data, vital signs, ECG.

Observation period

The observation period will be divided into 4 epochs:

- The **pre-treatment** epoch is defined as the time from the signed informed consent date up to the first administration of IMP.
- The **treatment** epoch is defined as the time from the first administration of the IMP to the last administration of the IMP + 7 days.
- The **residual treatment** epoch is defined as the time from the last administration of the IMP + 8 days to the last administration of the IMP + 84 days.

The treatment-emergent adverse event (TEAE) period will include both **treatment** and **residual treatment** epochs.

- The **post-treatment** epoch is defined as the period of time starting the day after the end of the TEAE period up to the end of the study (defined as last protocol-planned visit or last study assessment).

The on-study observation period is defined as the time from the first administration of IMP until the end of the study (defined as last protocol planned visit or last study assessment).

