	
• Tolerability at the IMP injection site:
- Erythema/redness (diameter and graded severity)- Swelling/induration/edema (diameter and graded severity)- Pain assessment. 
Immunogenicity:
 
• Testing for ADA 
Pharmacokinetics:
 
• SAR156597 plasma concentrations 
Biomarkers:
 
• Measurement of protein biomarkers associated with the activity of the disease (COMP, CCL2) and the IL-4/IL-13 pathway (TARC, periostin, and eotaxin-3).• Archived blood samples for future assays of protein and mRNA biomarkers related to the disease and the response to therapy (requires separate informed consent).
ASSESSMENT SCHEDULE	
The study will comprise 8 on-site visits AND 4 phone calls:
 
• Visits:
- V1 (screening visit) between Day -28 and Day -1.- V2 (baseline visit) at Day 1 (first dosing).- Treatment period: V3 at Week 2, V4 at Week 4, V5 at Week 8, V6 at Week 12, V7 at Week 24.- V8 (End-of-Study [EOS] visit) at Week 35.- A time window of ± 2 days will be allowed for each visit.• Phone calls:
- For safety considerations phone calls will be made at Week 6, 16 and 20 during the treatment period, and at Week 30 during the follow-up period.

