c Study treatment is to be administered once a week, either at the site or at home by a qualified healthcare professional – Last dose will be given at Week 23

d Complete physical examinations will include skin, nasal cavities, eyes, ears, respiratory, cardiovascular, gastrointestinal, neurological, lymphatic, and musculoskeletal systems. For the dermatological examination the Investigator should evaluate for SSc related skin changes and some specific findings that may indicate vasculitis including, but not limited to: purpura, papules or non-blanching rashes. Nail beds (periungual areas) should be examined for “splinter lesions” and digital tuft for tuft purpura or ischemia. Gynecological and urogenital examinations will not be done in this study unless for cause

e Vital signs, including blood pressure (mmHg), heart rate (beats per minute) and body weight (kg) will be measured at screening, baseline and every subsequent visit. Height (cm) will be measured at screening (Visit 1) only. BMI will be calculated automatically at all visits

- f* All abnormal ECG interpretation will be reviewed and confirmed by a local cardiologist.
- g* Previous echocardiogram may be used if obtained within 6 months of V1 (screening visit).
- h* Hematology: Hemoglobin, hematocrit, red blood cell count, erythrocyte sedimentation rate (ESR), white blood cell count with differential and platelet count. Biochemistry: Fasting glucose, blood urea nitrogen, creatinine, sodium, potassium, chloride, bicarbonate, calcium, phosphorous, total protein, albumin, total bilirubin, alkaline phosphatase, ALT, AST, CPK, hs CRP. Urinalysis (dipstick) to include: specific gravity, pH, glucose, ketones, blood, protein, nitrate, leukocyte esterase, urobilinogen and bilirubin. If any parameter on the dipstick is abnormal, a urine sample should be sent to the central laboratory for testing. If positive for protein and/or red blood cells, microscopic analysis will be performed by the central laboratory
- i* Serology testing includes HIV-1/HIV-2 antibody, hepatitis B surface antigen, hepatitis B surface antibody, hepatitis B core antibody, hepatitis B DNA (reflex to a positive hepatitis B core antibody), hepatitis C antibody and hepatitis C RNA (reflex to a positive hepatitis C antibody)
- j* [REDACTED]

- k* Tuberculosis screen: history and QuantiFERON-TB Gold test. If the result of the initial QuantiFERON-TB Gold test is indeterminate, the test should be repeated one time

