11.4.3 Analyses of safety data

The summary of safety results will be presented by treatment group actually received.

All safety analyses will be performed on the safety population using the following common rules:

- The baseline value is defined generally as the last available value before the first administration of the IMP.
- For quantitative safety parameters based on central laboratory/reading measurements, descriptive statistics will be used to summarize results and change from baseline values by visit and treatment group.
- The analysis of the safety variables will be descriptive and no hypothesis testing is planned.

The following definitions will be applied to laboratory parameters, vital signs, and ECG.

- The potentially clinically significant abnormality (PCSA) values are defined as abnormal values considered medically important by the Sponsor according to predefined criteria/thresholds based on literature review and defined by the Sponsor for clinical laboratory tests, vital signs, and ECG.
- PCSA criteria will determine which patients had at least 1 PCSA during the TEAE period, taking into account all evaluations performed during the TEAE period, including unscheduled or repeated evaluations. The number of all such patients will be the numerator for the TEAE PCSA percentage.

The TEAE period is defined as the time from the first administration of the IMP up to 12 weeks (84 days) from the last dose of IMP.

Please refer to [Section 9.2](#) for the safety endpoints.

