2.4.5 Analyses of safety data

The summary of safety results will be presented by treatment group.

General common rules

All safety analyses will be performed on the safety population as defined in [Section 2.3.2](#), unless otherwise specified, using the following common rules:

- Safety data in patients who do not belong to the safety population (eg, exposed but not randomized) will be listed separately.
- The baseline value is defined as the last available value before the first administration of the IMP.
- The potentially clinically significant abnormality (PCSA) values are defined as abnormal values considered medically important by the Sponsor according to predefined criteria/thresholds based on literature review and defined by the Sponsor for clinical laboratory tests, vital signs, and ECG (PCSA version dated May 2014 [[Appendix A](#)]).

- PCSA criteria will determine which patients had at least 1 PCSA during the TEAE period, taking into account all evaluations performed during the TEAE period, including unscheduled or repeated evaluations. The number of all such patients will be the numerator for the treatment-emergent PCSA percentage.
- The treatment-emergent PCSA denominator by group for a given parameter will be based on the number of patients assessed for that given parameter in the TEAE period by treatment group on the safety population.
- For quantitative safety parameters based on central laboratory/reading measurements, descriptive statistics will be used to summarize results and change from baseline values by visit (baseline and post-baseline time points) and treatment group. Summaries will include the last and the worst on-treatment value. Only data sampled before or on the day of the last IMP administration will be included in the analysis. The worst on-treatment value is defined as the nadir and/or the peak post-baseline before or on the day of the last IMP administration according to the direction (minimum or maximum) of the abnormality as defined in the PCSA list.
- All measurements (scheduled or unscheduled) will be assigned to time points according to analysis windows as defined in [Section 2.5.4](#).
- The analysis of the safety variables will be essentially descriptive and no systematic testing is planned. Relative risks versus placebo and their 95% confidence intervals may be provided, if relevant.

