- Listing of all Treatment emergent AESIs experienced per patient and by treatment arm: Patient ID, AESI category, PT, time to onset of event, date of first and last IMP administration, duration, intensity, corrective treatment, seriousness, relationship to SAR.

Analysis of pre-treatment and post-treatment adverse events

If any pre-treatment or post-treatment AE lead to death or any pre-treatment AE lead to treatment discontinuation, a listing will be provided.

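### The TEAE period closes on the nominal day of the Week 35 visit with no tolerance, so an in-window visit can fall outside it and late safety findings go uncounted

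*SAP*

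**What the plan says.** The two documents agree on the length of the TEAE period. Protocol 11.4.3 defines it as "the time from the first administration of the IMP up to 12 weeks (84 days) from the last dose of IMP". SAP 2.1.5 builds it from a treatment epoch and a residual epoch, the latter "from the last administration of the IMP + 8 days to the last administration of the IMP + 84 days". Everything later is post-treatment, an epoch "starting the day after the end of the TEAE period up to the end of the study".

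The schedule sits exactly on that limit. Footnote c of the flow chart (Protocol 1.2) states: "Last dose will be given at Week 23". V8 is at Week 35. The protocol synopsis adds: "A time window of ± 2 days will be allowed for each visit". Protocol 8.1.4 gives each weekly dose its own ±2 days, counted from the first dose. The TEAE period has no matching allowance.

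The safety outputs depend on it. SAP 2.4.5 states: "PCSA criteria will determine which patients had at least 1 PCSA during the TEAE period". The AESI table and listing in SAP 2.4.5.1 cover treatment-emergent events only. For events outside the period, that section specifies one output: "If any pre-treatment or post-treatment AE lead to death or any pre-treatment AE lead to treatment discontinuation, a listing will be provided". SAP 2.1.7 also uses the TEAE period to define ADA-positive patients.

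**The concern.** V8 is the only scheduled laboratory, ECG and vital-sign assessment after Week 24; the Week 30 contact is a phone call (Protocol 1.2). SAP 2.4.5 already keeps values taken after the last dose out of the quantitative summaries. That leaves PCSA incidence as the main planned summary table in which a non-liver V8 abnormality can appear. Whether it does depends on one day of scheduling, within windows the protocol allows.

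The PCSA denominator is patients assessed for the parameter during the TEAE period. A patient with earlier assessments therefore stays in the denominator while an abnormality at a late V8 does not reach the numerator. An ALT AESI, which SAP 2.1.5.1 selects from laboratory data, could be lost from the AESI table in the same way if it is dated by the sample.

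**Working it through.** **Inputs**
- First injection is Day 1 (SAP 2.5.1), so nominal day = 7 × week + 1.
- Last dose: Week 23, ±2 days (Protocol 1.2 and 8.1.4).
- V8: Week 35, ±2 days (Protocol synopsis and 1.2).
- TEAE end: last dose + 84 days (Protocol 11.4.3, SAP 2.1.5).

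**Reproducing the plan's figures**
- V8: 7 × 35 + 1 = Day 246, the target in SAP 2.5.4, Table 3.
- Last dose: 7 × 23 + 1 = Day 162.
- Gap: 246 − 162 = 84 days, the 12 weeks stated in SAP 2.1.6 for the follow-up sample.
- TEAE end: 162 + 84 = Day 246, the V8 target day.

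**Permitted gap**

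Let v be the deviation of V8 and d that of the last dose, each from −2 to +2 days. Gap = 84 + v − d, so it runs from 84 − 2 − 2 = 80 to 84 + 2 + 2 = 88 days. If only one of the two slips, it is 82 to 86. V8 falls outside the period when v > d.

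**Share outside**

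The documents give no distribution of deviations, so this part rests on assumption. For independent deviations, each symmetric about the target day, the share is (1 − P(v = d)) / 2. In the clustered rows the remaining probability is spread evenly over the other four days.

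| Assumed pattern, both dates | P(v = d) | Share outside |
|---|---|---|
| All on target | 1 | 0% |
| 90% on target | 0.81 + 4 × 0.025² = 0.8125 | 9.4% |
| 80% on target | 0.64 + 4 × 0.05² = 0.65 | 17.5% |
| 60% on target | 0.36 + 4 × 0.10² = 0.40 | 30% |
| Uniform over five days | 5 × 0.2² = 0.20 | 40% |

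Using the protocol's assumed 10% discontinuation, 94 × 0.9 = 84.6 patients complete treatment. The 9.4% and 40% rows then correspond to about 8 and 34 patients over both arms.

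**AE onset time lost**

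At most 4 days per patient. In the uniform case the mean is (4 × 1 + 3 × 2 + 2 × 3 + 1 × 4) / 25 = 0.8 day, and 0.8 / 246 = 0.3% of the nominal study duration.

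**What a V8 at +85 to +88 changes**

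| Output | Effect |
|---|---|
| General PCSA incidence, non-liver laboratory, vital signs, ECG (SAP 2.4.5) | V8 values not counted |
| TEAE and AESI tables (SAP 2.4.5.1) | Lost only if first dated after +84 |
| Liver PCSA display (SAP 2.4.5.3) | None: it uses any post-baseline visit |
| Last and worst on-treatment summaries | None: V8 is already excluded |
| Laboratory, vital-sign and ECG listings with PCSA flags (SAP 2.4.5.3 to 2.4.5.5) | None: no TEAE limit is stated |
| ADA-positive patient (SAP 2.1.7) | A first-positive V8 sample does not qualify |
| Treatment-emergent ADA (SAP 2.1.7) | The same sample qualifies: the definition runs to the follow-up visit |

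**The case against.** A cut-off fixed to the last dose and identical in both documents is a legitimate choice. With the half-life of about 15 days given in Protocol section 4, 84 days is 84 / 15 = 5.6 half-lives. Nor does the plan require V8 to lie inside the TEAE period: patients who stop treatment early still attend V8, often well beyond +84 days. A reader might infer that Week 35 was chosen so that V8 would close the TEAE period, but neither document says so.

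A reader might also infer that a late V8 removes all its data from the safety tables. The documents do not support that. SAP 2.1.5.1 classes AEs by when they developed, worsened or became serious, not by visit date, and SAP 2.5.3 treats an incomplete onset date as treatment-emergent unless the information shows otherwise. Liver values stay in the liver display, flagged listings still show V8 values, and SAP 2.4.7 summarises ADA from all samples. SAP 2.4.5.1 also says post-treatment AEs will be described separately, although the only output it specifies is the listing quoted above.

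These points limit the size of the problem and stand. They do not return late V8 non-liver laboratory, ECG or vital-sign values to the PCSA incidence tables, and they do not reconcile the two ADA definitions. The half-life argument supports a period of about 12 weeks. It does not explain a limit with no tolerance on the only scheduled follow-up laboratory and ECG visit. The listing of all SAEs in Protocol 11.4.3.1 is a partial backstop, but SAP 2.4.5.1 restricts the SAE listing to the TEAE period.

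**Conclusion.** The point holds as a boundary problem of modest size. The TEAE limit and the V8 target coincide at Day 246, and permitted slippage puts V8 up to 4 days past the limit. The consequences are confined to non-liver PCSA incidence, AEs and AESIs first dated in those 1 to 4 days, and the ADA-positive label.

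The 40% should not be read as an expected loss: it requires uniform deviations. Dates clustered on target give about 9% to 30%, and exact adherence gives 0%. Dose and visit dates that slip together would lower the share further. These are shares of completers whose V8 falls outside the period. The number whose first PCSA or AESI occurs at such a visit is smaller and cannot be estimated from the documents.

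A reader might infer a biased treatment comparison. Nothing in the documents shows one: both arms share the same schedule and windows, so the likely effect is similar under-counting of late findings in each. This is a cheap improvement, not a threat to the safety conclusions.

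**What to change.** In SAP 2.1.5 and Protocol 11.4.3, end the TEAE period at the later of (a) last IMP + 84 days and (b) the date of V8, where V8 is within 88 days of the last IMP. The 88 days is the largest in-window gap. Under the uniform assumption a fixed cut-off at +85, +86 or +87 would still leave 24%, 12% or 4% of V8 visits outside, against none at +88.

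Apply the same end date wherever the limit is used: PCSAs and AESIs, the ADA-positive definition in SAP 2.1.7, the split between concomitant and post-treatment medication in SAP 2.1.2, and the TEAE definition in the protocol synopsis.

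The cost is a short wording change in several places and a TEAE period up to 4 days longer for some completers. No new data are needed. Patients who stop early and attend V8 more than 88 days after their last dose are classified as before.
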